8.3.2	EC/IRB Notification by Investigator	15
8.3.3	FDA Notification by Sponsor	16
SERIOUS ADVERSE EVENTS NOT CONSTITUTING UNANTICIPATED PROBLEMS ARE TO BE REPORTED TO THE HICCC DSMC. REPORTING SHOULD OCCUR WITHIN 24 HOURS OF KNOWLEDGE OF THE SAE OCCURRING AT OUR INSTITUTION OR AFFILIATE SITES.		17
8.4	UNBLINDING PROCEDURES	17
8.5	STOPPING RULES.....	17
8.6	MEDICAL MONITORING.....	17
8.6.1	Internal Data and Safety Monitoring Board	17
8.6.2	Independent Data and Safety Monitoring Committee	18
9	DATA HANDLING AND RECORD KEEPING	17
9.1	CONFIDENTIALITY.....	17
9.2	SOURCE DOCUMENTS.....	18
9.3	CASE REPORT FORMS.....	18
9.4	RECORDS RETENTION	18
10	STUDY MONITORING, AUDITING, AND INSPECTING	18
10.1	STUDY MONITORING PLAN	18
10.2	AUDITING AND INSPECTING.....	19
11	ETHICAL CONSIDERATIONS	19
12	STUDY FINANCES	19
12.1	FUNDING SOURCE	19
12.2	CONFLICT OF INTEREST	19
12.3	SUBJECT STIPENDS OR PAYMENTS	20
13	PUBLICATION PLAN	20

CONFIDENTIAL

This material is the property of [name]. Do not disclose or use except as authorized in writing by the study sponsor

List of Abbreviations

DCIS: ductal carcinoma in situ

IM: intramuscular

IV: intravenous

miR: microRNA

NAF: nipple aspirate fluid

PK: pharmacokinetic

SQ: subcutaneous

CONFIDENTIAL

This material is the property of [name]. Do not disclose or use except as authorized in writing by the study sponsor

Study Summary

Title	INTRANASAL OXYTOCIN USE IN IDENTIFYING THE MICRO-RNA FINGERPRINT IN NAF, SERUM, AND TISSUE IN PATIENTS WITH DCIS OR INVASIVE BREAST CANCER
Short Title	Oxytocin, microRNA and breast cancer
Protocol Number	IRB-AAAL5203
Phase	Pilot
Methodology	Pilot proof of principle study
Study Duration	1 year
Study Center(s)	Columbia University Medical Center
Objectives	To determine the feasibility of assessing miR profiles in NAF, serum and tissue of women diagnosed with DCIS or invasive breast cancer
Number of Subjects	40
Diagnosis and Main Inclusion Criteria	Patients with DCIS or invasive breast cancer scheduled for breast surgery at Columbia Medical Center
Study Product, Dose, Route, Regimen	Oxytocin (Syntocinon Spray), 4 IU (1 spray) per nostril, intranasal route, prior to nipple aspirate fluid collection
Duration of administration	Once before NAF is collected
Reference therapy	None
Statistical Methodology	Calculation of presence of miRs compared to normative reference population, binomial test to determine significant differences, Benjamin Hochberg procedure to rule out false positives, and ranking of miRs by p-value to determine most favorable biomarkers.

CONFIDENTIAL

This material is the property of [name]. Do not disclose or use except as authorized in writing by the study sponsor

1 Introduction

This document is a protocol for a human research study. This study is to be conducted according to US and international standards of Good Clinical Practice (FDA Title 21 part 312 and International Conference on Harmonization guidelines), applicable government regulations and Institutional research policies and procedures.

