3.1 General Design

We propose a pilot proof of principle study to assess and compare the miR fingerprint (or profile) in NAF, serum, and tissue from patients undergoing a lumpectomy or mastectomy for in situ or invasive breast cancer. As this study is a proof of concept there is no power presented. Other than the collection of NAF, treatment will not vary from the standard of care. The collection of all specimen types will be completed within the regularly scheduled operative time period. The surgery will not be prolonged in any way for specimen collection. Forty patients (20 with DCIS, 20 with invasive breast cancer) will be entered into the study. A total of 5 patients will also undergo pharmacokinetic (PK) draws during the time of surgery to assess the baseline oxytocin level. All other subjects enrolled will be enrolled into the “non-PK” cohort. Patients receiving care at the Breast Surgery Department at Columbia who meet criteria will be offered participation in the study. Patients will answer a brief questionnaire preoperatively. At the time of surgery patients will undergo a blood draw as well as collection of NAF (via prior administration of intranasal oxytocin, gentle massage, aspirator, and breast pump from both breasts). The NAF and blood samples will be sent to the pathology lab for analysis of miR profile. At the completion of the case, the breast tissue will be sent to pathology per routine. Once in pathology, 5 paraffin-embedded slices will be created to evaluate for miR profile. Serum, NAF, and tissue will be analyzed for their miR profile.

Once total RNA is extracted from the biological samples it will be processed to fluorescently label the microRNAs species according to the V2-Human microRNA array (Agilent). MicroRNA profiling will be obtained and analyzed using the gene-spring software analysis package. First, expression and cluster analysis will be performed to identify the microRNA that are expressed in our samples and to classify them accordingly to their expression. Then, the predicted targets of the over/down-regulated microRNAs will be identified using target prediction bioinformatics tools (TargetScan, Miranda and Pictarvert). Finally, statistical studies between over/under-represented microRNAs will be performed.

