7.1 Sample Size Consideration

Contralateral breast without disease will serve as the control. In a sample of 40 patients with unilateral disease, we expect 60% of the patients to show significantly altered expression of miRNAs in the diseased breast as compared to the breast without disease for the test to be of clinical relevance. Ideally a detectable difference would be the difference between a null hypothesis of 0% and an alternative of 60% or a second alternative of 35%. Since this study is the first of its kind, we will consider the test to be not clinically relevant if less than 35% of patients show significantly altered expression miRNA in the diseased breast as compared to the breast without disease.

Using a two sample z-test, type I error of 0.05, and a two-sided significance level, a sample size of 40 will have greater than 80% power to detect a difference between a null hypothesis of 35% and an alternative hypothesis of 60%.

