7.2 Statistical Methods

The primary analysis will be conducted to determine the presence and expression levels of 800 miRNA's among DCIS and invasive breast cancer patients. Based on the resulting profiles, we will determine whether or not its expression for each miRNA from the tumor side differs from that of the normal side.

We will interrogate 800 miRNAs. The vast majority will not be expressed in any sample. A minority will be measurable/detectable in some samples and a smaller minority will be detectable in all samples.

The presence of miRNA can be as follows:

- a. Present in tumor and absent in normal
- b. Present in normal and absent in tumor
- c. Present at high level in tumor and low level in normal
- d. Present at high level in normal side and low level in tumor.

Of these a and c are most important and relevant for our analysis. If even a single miRNA is absent in tumor and present in 30% of cancers or if there is at least one miRNA out of these 800 that is present at low levels in all "normals" and high levels in 30% of tumors that would be a "success". We will dichotomize to low and high levels of miRNA to calculate frequencies and the associated risk estimates and 95% confidence intervals. The comparison of proportions will be performed using two-sample z-tests.

CONFIDENTIAL

This material is the property of [name]. Do not disclose or use except as authorized in writing by the study sponsor

7.3 *Subject Population(s) for Analysis*

Patients diagnosed with DCIS or invasive breast cancer.

8 Safety and Adverse Events

8.1 *Definitions*

Adverse Event

An ***adverse event*** (AE) is any symptom, sign, illness or experience that develops or worsens in severity during the course of the study. Intercurrent illnesses or injuries should be regarded as adverse events. Abnormal results of diagnostic procedures are considered to be adverse events if the abnormality:

- results in study withdrawal
- is associated with a serious adverse event
- is associated with clinical signs or symptoms
- leads to additional treatment or to further diagnostic tests
- is considered by the investigator to be of clinical significance

Serious Adverse Event

Adverse events are classified as serious or non-serious. A ***serious adverse event*** is any AE that is:

- fatal
- life-threatening
- requires or prolongs hospital stay
- results in persistent or significant disability or incapacity
- a congenital anomaly or birth defect
- an important medical event

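### Read in the usual way, the Study Summary's binomial test against a reference frequency ignores the reference's sampling error and gives p = 0 to a miRNA seen in one patient and never in the reference

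*Combined protocol and SAP*

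**What the plan says.** The Statistical Methodology row of the Study Summary is the only place that sets out how biomarkers are selected. It begins with "Calculation of presence of miRs compared to normative reference population, binomial test to determine significant differences" and continues with "Benjamin Hochberg procedure to rule out false positives, and ranking of miRs by p-value to determine most favorable biomarkers". It does not say what the "normative reference population" is, how large it is, what null proportion is tested, whether the test is one- or two-sided, or what false discovery level applies.

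Section 7 describes a different comparison. Section 7.1 states: "Contralateral breast without disease will serve as the control". Section 7.2 compares proportions by two-sample z-tests and mentions no binomial test, external reference, multiplicity procedure or ranking. On the number of miRNAs it says: "We will interrogate 800 miRNAs. The vast majority will not be expressed in any sample". It adds that a minority will be detectable in some samples.

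Section 3.1 gives the sample size: "Forty patients (20 with DCIS, 20 with invasive breast cancer) will be entered into the study".

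**The concern.** The scientific question is whether a miRNA is present equally often in patients and in the reference. A one-sample binomial test asks something narrower: whether the patients' true rate equals the observed reference proportion, taken as exact. If the reference is small, its observed proportion is itself an estimate, and leaving out that error makes the p-values too small.

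The extreme case is an observed reference proportion of 0. The null distribution then puts all its mass on zero detections, so a single detection has probability 0.

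Benjamini-Hochberg assumes valid p-values and cannot repair invalid ones, and a p-value of 0 passes at any level. What is at stake is the list of most favorable biomarkers: single-patient detections could be declared significant and placed above markers that reach the 30% mark in Section 7.2.

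**Working it through.** **The plan's own figure.** The Summary's test has no stated operating characteristic to reproduce. The only computed statistical figure is in Section 7.1, where 40 patients "will have greater than 80% power to detect a difference between a null hypothesis of 35% and an alternative hypothesis of 60"%. A one-sample z calculation supports it: (0.25 − 1.96·√(0.35·0.65/40)) / √(0.60·0.40/40) = 1.32, a power of 90.6%. The two-sample z-test named there, with 40 per group, gives 61.3%. That is a separate matter and nothing below depends on it.

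**Inputs.**
- Patients: n = 40 (Section 3.1). Sensitivity case: n = 31, from the 77% bilateral NAF yield in Section 2 (0.77 × 40 = 30.8).
- Level: two-sided 0.05, which Section 7.1 states for the z-test. Carrying it over to the binomial test is an assumption.
- Reference size m: not in the documents, so a range is shown.
- Null: p0 = observed reference count / m. This is the usual reading, not a stated rule.

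**Single cases.** The p-value is the total probability, under Bin(40, p0), of outcomes no more likely than the one observed. The alternatives count both groups' error; for McNemar, all detections are taken as discordant pairs.

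| Patients | Reference | One-sample binomial | Fisher exact | Exact McNemar |
|---|---|---|---|---|
| 0/40 | 0 | 1 | 1 | 1 |
| 1/40 | 0/40 | 0 | 1.0 | 1.0 |
| 12/40 | 1/40 | 1.7e-10 | 0.0015 | 2·(1 + 13)/2^13 = 0.0034 |

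The one-sample test ranks the single detection first. Both alternatives reverse that order.

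**Type I error.** For each reference count j, with j ~ Bin(m, p), test k ~ Bin(40, p) against p0 = j/m, using the same true p in both groups, and average the rejection probability over j and k. Groups are independent, p runs from 1% to 50%, and Benjamini-Hochberg is not yet applied.

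| Reference size m | Rejection rate at nominal 5% |
|---|---|
| 20 | 24-40% |
| 40 | 15-25% |
| 100 | 8-13% |
| 200 | 5-6.5% |
| 500 | about 3-5% |

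With n = 31 and m = 40 the range is 14-22%. Fisher's test at n = m = 40 stays between 0 and 3.3%.

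**After Benjamini-Hochberg.** The level (q = 0.05) and the mix of detection rates are assumptions. Take 800 miRNAs with no true difference: 600 never present, 150 present in 1-50% of samples and 50 always present. Simulation then gives at least one false discovery in 98% of runs for m = 40 (mean 5.0 miRNAs), 52% for m = 100 and about 1% for m = 500. Fisher's test at m = 40 gave none in 100 runs.

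**How far p = 0 persists.** The chance that a miRNA with equal true rate p in both groups gets p = 0 by this route is (1 − p)^m · [1 − (1 − p)^40].
- p = 2%, m = 40: 0.446 × 0.554 = 24.7%.
- p = 10%, m = 40: 0.0148 × 0.985 = 1.5%.
- p = 0.2%, m = 400: 0.449 × 0.077 = 3.5%.

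A larger reference therefore removes most of the general inflation, but not this result for rarely detected miRNAs.

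**If the reference is the paired breast.** A normal approximation, P(|Z| > 1.96/√(2(1 − ρ))), gives 17% at within-woman correlation ρ = 0, 11% at 0.25 and 5% at 0.5. Simulated paired data (n = 40, true rates 1-50%) gave 9-21% at ρ = 0.25 and 4-15% at ρ = 0.5, with the excess at rare frequencies. When every normal breast is negative, p0 = 0 and the p = 0 result remains.

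**The case against.** The strongest reply is that the plan never says the null is the observed reference frequency treated as fixed. That is an inference from one Summary line. With the paired control of Section 7.1, a binomial test could even mean the exact test on discordant pairs, which is valid. This stands, and it makes the point conditional. But the line speaks of presence compared with a normative population, which fits the one-sample reading better, and nothing in the plan rules that reading out.

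A reader might infer that the plan would deliver 15-25% false positives. The documents do not support that. The figure needs a reference of 40, which borrows the contralateral breasts from Section 7.1, and where that control is named the test is a two-sample z-test that counts both groups' error. It is also a per-miRNA rate before Benjamini-Hochberg and assumes independent groups.

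A reader might also infer that most of the 800 miRNAs are exposed to p = 0, because most are expected not to be expressed. They are not: 0/40 against a reference of 0 gives p = 1. Exposure needs absence from the whole reference together with detection in some patient.

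Finally, this is a pilot with a feasibility endpoint, and a 1/40 detection cannot meet the 30% success mark in Section 7.2. That limits the harm to the significance list and the ranking, which are nevertheless what the Summary promises.

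**Conclusion.** The point holds conditionally. If the Summary line governs selection and is run as a one-sample test at the observed reference frequency, its p-values are not valid inputs to Benjamini-Hochberg or to the ranking. The p = 0 result for sporadically detected miRNAs is certain under that reading whenever the reference shows none. The general inflation depends on a reference size that the documents do not give: serious at 20 to 40, moderate at 100, small at 200 and essentially absent at 500, for independent groups. Positive pairing reduces it.

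Section 7.2's z-test does not share the defect, but that section supplies no multiplicity or ranking step, so Section 7 does not replace the Summary's selection procedure. The change is worth making before any data are analyzed because it is cheap and removes the ambiguity.

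**What to change.** In the Study Summary, replace the binomial test against a reference frequency. For the contralateral comparison of Section 7.1, use the exact binomial test on discordant pairs with null probability 0.5 (exact McNemar). If an external normative set is kept, state its source and size and compare the two observed counts by Fisher's exact test. Feed these p-values into Benjamini-Hochberg at a stated level, then into the ranking, and say the same in Section 7.2.

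The cost is one sentence in each place, with no extra patients, samples or assays. The downside is larger p-values, so fewer miRNAs will be called significant. Against 0/40 in an external reference, Fisher needs 6/40 to pass 0.05 unadjusted (p = 0.026; 5/40 gives 0.055). If one miRNA were the only signal among 800, Benjamini-Hochberg at an assumed q = 0.05 would require p ≤ 0.05/800 = 6.25e-5. Exact McNemar with 12 discordant pairs all in one direction gives 2 × 0.5^12 = 0.00049 and would not pass; 15 such pairs (2 × 0.5^15 = 6.1e-5) would. The sponsor should accept that limit knowingly.

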1.1 Background

Breast cancer is the leading cause of cancer death among women. In 2008 alone, 458,400 deaths worldwide were due to breast cancer and more than 1.3 million women were newly diagnosed with breast cancer.¹ Presently, the best and most widely accepted tool that we have to screen for breast cancer is the mammogram. However, this modality remains radiation-based, is uncomfortable for patients, and has a maximum sensitivity of 70-90%. The other main methods of detection include physical exam, ultrasound and MRI, each of which has its own set of limitations. Physical exam requires a palpable lesion, which may hinder early diagnoses. Ultrasound is time-consuming and highly operator-dependent. MRI is costly, lacks specificity and is not covered by insurance for non-high risk patients.

As an alternative, we propose the use of NAF from breast cancer patients as a way to identify microRNA profiles. Considering 90% of breast cancers originate from ductal epithelium, it is possible that cells and secretions collected from such ducts would allow for earlier detection of breast cancer. The collection of NAF is furthermore appealing because it is a non-invasive method of obtaining specimens. Ideally, NAF would be used to identify biomarkers that predict the risk of breast cancer and/or detect breast cancer in its early stages.^{2,3,4} To date, cellular atypia, DNA methylation and proteins have all been studied in aspirate fluid.^{5,6} Our pilot appears to be the first to successfully extract and analyze miR from NAF.

MiRs are small, 20-nucleotide non-coding RNAs that modulate messenger RNA transcription, leading to changes in tumor suppression and oncogenic expression.⁷ They tend to be more stable than protein markers, detectable in small quantities both inside and outside of cells.⁸

¹ Jemal, Ahedin, Freddie Bray, Melissa M. Center, Jacques Ferlay, Elizabeth Ward, and David Forman. "Global Cancer Statistics." *CA: A Cancer Journal for Clinicians* 61.2 (2011): 69-90.

² Calin, G. A. "MicroRNA Profiling Reveals Distinct Signatures in B Cell Chronic Lymphocytic Leukemias." *Proceedings of the National Academy of Sciences* 101.32 (2004): 11755-11760.

³ Calin, G. A. "Human MicroRNA Genes Are Frequently Located at Fragile Sites and Genomic Regions Involved in Cancers." *Proceedings of the National Academy of Sciences* 101.9 (2004): 2999-3004.

1.3 Preclinical Data

Oxytocin has long been studied in animals, and continues to be prescribed today by veterinarians. The IV, IM and subcutaneous (SQ) forms are indicated for obstetrical use and milk letdown in cows and sows.¹⁹ Many studies over the past several decades support the drug’s use in promoting animal lactation. Exogenous oxytocin has been shown to increase milk letdown in animals as well as enhance milk production.^{19,20,21} Animal toxicity effects based on a few isolated experiments include fetal growth stimulation and leftward shift of the fetal oxygen dissociation curve.²² To date, there do not appear to be other significant side effects studied in animals exposed to exogenous oxytocin.

One group at UCLA (Zhang et al., 2003) studied nasal oxytocin in 9 healthy, non-lactating female volunteers between the ages of 19-41. NAF collection before and after 25U oxytocin per nostril showed a significant increase in volume of $1.39 \pm 2.2\mu\text{L}$ ($p = 0.0116$). Six breasts that did not release NAF initially did so following oxytocin administration. Pregnant women were excluded from the study because of the potential for abnormal uterine contractions; however, no adverse events were noted.¹⁴

Several important oxytocin experiments were recently completed in Europe by van Diest et al. In the first of a series (Suijkerbuijk, 2007), oxytocin-supported nipple aspiration was successful in 63 of 67 healthy female volunteers. This rate (94%) was overwhelmingly greater than those reported in previous studies not using oxytocin, which ranged from 39-66%.^{23,24} A subgroup analysis determined that there was sufficient material for genetic, epigenetic and proteomic characterizations. Again, there were no side effects reported, with 66/67 women who would be willing to repeat the procedure and an average discomfort rating of 1.3 on a scale of 0-10.²⁵

A follow-up study was published in 2010 by the same group (Suijkerbuijk, 2010). It demonstrated a similar effect of intranasal oxytocin on 90 patients at high risk for breast cancer. NAF was successfully collected from 90% of the subjects, with a mean discomfort rating of 0.6 (mammography averages 4.9, MRI 2.6). A subgroup analysis among 50 patients showed that quantitative multiplex methylation-specific PCR was able to be performed on 100% of the samples, suggesting the utility of NAF in biomarker identification.¹⁶

Studies using intranasal oxytocin have also become increasingly common in the field of psychiatry. Intranasal oxytocin has been shown to increase sociability and decrease anxiety in both animals and human subjects.^{26,27} Several IND exemptions for Syntocinon Spray have been

²³ Fabian, C. J. "Breast-tissue Sampling for Risk Assessment and Prevention." *Endocrine Related Cancer* 12.2 (2005): 185-213.

²⁴ Wrensch, Margaret R., Nicholas L. Petrakis, Larry D. Gruenke, Virginia L. Ernster, Rei Miike, Eileen B. King, and Walter W. Hauck. "Factors Associated with Obtaining Nipple Aspirate Fluid: Analysis of 1428 Women and Literature Review." *Breast Cancer Research and Treatment* 15.1 (1990): 39-51.

1.5 Dose Rationale and Risk/Benefits

Based on prior studies in non-lactating women, we plan to administer one spray (4 IU) per nostril 15-30 minutes before NAF collection. The benefits will be greater NAF yield for miR analysis. The risks include rare anaphylactic reactions, common headache, tachycardia or bradycardia, uncommon arrhythmia, very rare hypertension, common nausea and vomiting, rare rash and allergic dermatitis, and uncommon abnormal uterine contractions. Because of the possibility of abnormal uterine contractions, pregnant women will be excluded in the study. [Frequency: *Very common* (> 1/10); *common* (> 1/100 to < 1/10); *uncommon* (> 1/1000 to < 1/100); *rare* (> 1/10 000 to < 1/1000); *very rare* (< 1/10 000), including isolated cases.]

2 Study Objectives

The main objective of this study is to demonstrate the feasibility of characterizing miR profiles in the NAF, serum and tissue of patients with DCIS or invasive breast cancer. Each set of miRs will be assessed for correlation with tumor presence. Tissue and serum are expected to be acquired from all patients. With the addition of intranasal oxytocin, bilateral NAF collection of adequate volume for analysis is expected from 77% of participants at increased risk for breast cancer.¹⁶

Analysis of the miR profiles will include comparisons among the different biological samples (tissue, serum, NAF) in order to understand their relationships with one another. We hypothesize that cancer subtypes will be identifiable by unique miR fingerprints, with the goal of creating a breast cancer screening tool.

²⁸ Pedersen, Cort A., and David L. Penn. "Oxytocin Treatment of Social Cognitive and Functional Deficits in Schizophrenia - Full Text View - ClinicalTrials.gov." *Oxytocin Treatment of Social Cognitive and Functional Deficits in Schizophrenia - Full Text View - ClinicalTrials.gov*. National Institute of Mental Health, n.d. Web. <<http://clinicaltrials.gov/ct2/show/NCT01394471>>.

²⁹ Guastella, Adam J., Stewart L. Einfeld, Kylie M. Gray, Nicole J. Rinehart, Bruce J. Tonge, Timothy J. Lambert, and Ian B. Hickie. "Intranasal Oxytocin Improves Emotion Recognition for Youth with Autism Spectrum Disorders." *Biological Psychiatry* 67.7 (2010): 692-694.

³⁰ Simeon, D., J. Bartz, H. Hamilton, S. Crystal, A. Braun, S. Ketay, and E. Hollander. "Oxytocin Administration Attenuates Stress Reactivity in Borderline Personality Disorder: A Pilot Study." *Psychoneuroendocrinology* 36.9 (2011): 1418-421.

Our aim is to first demonstrate proof of principle. We would like to extend our initial trial by 1 year since the NAF volumes were inadequate without pharmacologic enhancement. Specifically, we were able to collect NAF from 13/40 patients, of which 8 were successfully analyzed for miR. To remedy this problem, we propose collecting additional specimens in the setting of intranasal oxytocin. This project will establish a foundation from which future miR analysis may be completed.

3 Study Design

